## 11 SAFETY ANALYSIS

Safety analyses are based on the Safety population. Safety analyses will be performed in the adult and the pediatric population separately and in the overall population (adult and pediatric populations combined).

### 11.1 Adverse Events

All reported AEs will be coded and summarized by system organ class (SOC) and preferred term (PT) according to MedDRA.

AE causality will be classified and assessed by the investigator. If the causality is definitive, probable, possible, or doubtful/unlikely, the event will be defined as a suspected adverse drug reaction (ADR). If the causal relationship is labeled as “Unrelated”, then it will be considered that the AE is not imputable to the investigational medicinal product and it is not a suspected ADR. In the framework of this study, a suspected ADR with a causal relationship of “definite” are named as adverse reaction. Adverse reactions are a subset of suspected ADR.

For summary purposes, AEs will be classified as treatment emergent AEs (TEAEs) or non-treatment emergent AEs (non-TEAEs) depending on the comparison of AE onset date/time with the start of study treatment. A TEAE will be defined as an AE which occurred on or after the start of study treatment. For AEs with incomplete start dates, the same algorithm for missing or partial date information described in Section 8.1 (Prior and Concomitant

Medication) will be used for determination of treatment emergent or not. Non-TEAEs and TEAEs will be summarized separately.

The incidence of AEs, suspected ADRs, non-serious AEs, SAEs, and AEs by severity and causal-relationship to the IP will be summarized using descriptive statistics. At each level of summarization, a subject will only be counted once per SOC or PT using the most severe or highest causal relationship AE. Subjects with deaths, SAEs, and AEs leading to premature discontinuation from the study will be listed.

Temporally-associated AEs defined as during infusion or within 24 hours and within 72 hours following the end of IP infusion will be separately summarized. For AEs that occur during study drug infusion, the infusion rate in effect at the time of onset of the AE, the time when the AE is first reported and the time when the AE changes materially in intensity and/or resolves will be listed.

Adverse events of special interest including allergic/hypersensitivity reactions and arterial and venous thrombotic events according to International Classification of Diseases, Ninth Revision, Clinical Modification (ICD-9-CM) will be separately summarized. The results of the Wells Score utilized to assess thrombotic events risk will also be listed.

All AEs will be presented in a data listing.

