8.3.1 ADVERSE EVENT

An AE is defined as any untoward medical occurrence in a subject or clinical investigation subject administered a medicinal product or study treatment and which does not necessarily have a causal relationship with this administration. An AE can therefore be any unfavorable and unintended sign (including any abnormal laboratory findings, for instance), symptoms, or disease temporally associated with the use of a medicinal product or study treatment, whether or not considered related to the medicinal product or study treatment.

Any AE that occurs at any time between signature of the informed consent and last day of the subject's participation in the clinical safety period of the study (Week 4 Visit) must be reported on the AE CRF/eCRF entry.

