8.3.2 CAUSALITY OF ADVERSE EVENT

The investigator will be asked to assess the causal relationship of the AE to the study treatment according to the following classification based on Karch FE et al [64]:

- **Definite:** An event that follows a reasonable temporal sequence from administration of the treatment or in which the treatment level has been established in body fluids or tissues; that follows a known response pattern to the suspected treatment; and that is confirmed by improvement on stopping the treatment (dechallenge), and reappearance of the event on repeated exposure (rechallenge).
- **Probable:** An event that follows a reasonable temporal sequence from administration of the treatment; that follows a known response pattern to the suspected treatment; that is confirmed by dechallenge; and that could not be reasonably explained by the known characteristics of the subject's clinical state.
- **Possible:** An event that follows a reasonable temporal sequence from administration of the treatment; that follows a known response pattern to the suspected treatment; but that could have been produced by the subject's clinical state or other modes of therapy administered to the subject.
- **Doubtful/Unlikely:** An event that follows a reasonable temporal sequence from administration of the treatment; that does not follow a known response pattern to the suspected treatment; but that could not be reasonably explained by the known characteristics of the subject's clinical state.
- **Unrelated:** Any event that does not meet the criteria above.

The operational tool to decide the AE causal relationship is based on algorithms by Karch-Lasagna and Naranjo [64-65].

When an AE is classified, assessing causal relationship by the investigator, as definitive, probable, possible, or doubtful/unlikely, the event will be defined as suspected adverse drug

reaction (ADR). When the causal relationship is labeled “Unrelated”, then it will be considered that the AE is not imputable to the study treatment and it is not an ADR.

Any AE experienced by the subject prior to the investigational product infusion on Day 0 will be labeled as Unrelated to the investigational medicinal product.

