** Causality assessment will be only made when the AE occurs after the subject has been administered the investigational product (at any dose). AE occurring before subject's exposure to study treatment will be always labeled as "Unrelated".*

In addition to the investigator's own description of the AEs, each AE will be encoded by the sponsor or designated (eg, contract research organization [CRO]) according to the Medical Dictionary for Regulatory Activities (MedDRA®) dictionary of medical codes.

A pregnancy not verified before enrollment but occurring during the course of the study will not be considered an AE, unless a causal relationship to the study drug is at least suspected. In any case, a Pregnancy Report Form must be completed and sent within 24

hours to the sponsor. A copy of the form should be filled at the study site for follow-up until the end of the pregnancy.

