9.1.4 STATISTICAL ANALYSIS OF SAFETY

Adverse events:

Safety analyses for FIB Grifols will be performed on the overall population (both adult and pediatric age groups). FIB Grifols safety will also be assessed independently for both adult and pediatric populations.

Any AE that occurs at any time between signing of the *Clinical Trial Informed Consent* and Week 4 Visit will be reported on the appropriate subject's CRF/eCRF entry for any subject who received at least 1 infusion (at any dose) of investigational product.

Treatment-emergent AEs (ie, AEs occurring after the start of the investigational product infusion) will be listed and tabulated by body system with subject identification code, and they will be also presented as subject incidences and percentages. In addition, treatment-emergent AEs will be summarized by both adult and pediatric populations as well as severity (intensity), seriousness (serious versus non-serious), and causal-relationship to the study product.

Similarly, all treatment-emergent AEs potentially related to the investigational product will be listed and tabulated by body system with subject identification code, and they will be also presented as subject incidences and percentages. In addition, these will be also summarized by both adult and pediatric populations as well as severity (intensity) and seriousness (serious versus non-serious).

For AEs temporally associated to the infusion, listings of AEs will be presented. AEs will be also split between AEs occurring during the infusion or after the infusion completion but within 24 and 72 hours after completion of the infusion. For an AE that occurs during an infusion, the infusion rate in effect at the time of onset of the AE, the time the AE is first reported and the time the AE changes materially in intensity and/or resolves are all to be reported and tabulated.

Subjects who die, report a serious AE (SAE), or withdraw from the study because of AEs will be also individually listed and summarized.

AEs will be coded according to the AEs classification of the MedDRA, and will be described by a synonym (Preferred Term) and the affected organ / system, the intensity, causality and seriousness.

Vital signs:

Vital signs (T, RR, HR, SBP, DBP) will be listed for each clinical trial subject. In case a subject presents a clinically relevant variation of vital signs during an infusion will be flagged and discussed as an AE temporally associated to the infusion.

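### TEAEs are defined by onset alone and AEs with pre-infusion onset are labelled Unrelated, so a pre-existing AE that worsens after infusion and stays on one record is left out of the TEAE and suspected-ADR summaries

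*SAP*

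**What the plan says.** **Treatment emergence.** SAP 11.1 sorts AEs into treatment-emergent and non-treatment-emergent "depending on the comparison of AE onset date/time with the start of study treatment", and then gives the definition: "A TEAE will be defined as an AE which occurred on or after the start of study treatment". Protocol 9.1.4 has the same content: "Treatment-emergent AEs (ie, AEs occurring after the start of the investigational product infusion". Neither text has a clause for worsening.

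**Causality.** Protocol 8.3.2: "Any AE experienced by the subject prior to the investigational product infusion on Day 0 will be labeled as Unrelated". The footnote in Protocol 8.3.6 says "Causality assessment will be only made when the AE occurs after the subject has been administered the investigational product", and adds "AE occurring before subject's exposure to study treatment will be always labeled as" Unrelated. SAP 11.1 draws the consequence for an event with that label: "it will be considered that the AE is not imputable to the investigational medicinal product and it is not a suspected ADR".

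**Collection window.** Protocol 8.3.1 collects "Any AE that occurs at any time between signature of the informed consent and last day of the subject's participation" in the clinical safety period, which ends at Week 4. Consent is taken at the Screening Visit, which may be up to 21 days before Day 0 (Protocol 4.6).

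**The concern.** AEs are recorded before the infusion, so some may be ongoing when it starts. If one of them then gets worse, the worsening is the part that could be due to the product. The plan fixes both the treatment-emergent status and the causality of the event by its first onset, and neither is revisited.

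This is the first use of the product in humans (Protocol 2.2). The safety sample is about 22 subjects, and an interim safety analysis in adults precedes pediatric enrolment (Protocol 9.1.5, SAP 4.4). In a sample of that size one event more or less changes the tables visibly. The scenario is also plausible. Protocol 2.3 names chills, fever, nausea and vomiting as reactions to fibrinogen concentrates, and symptoms of that kind can also be present beforehand for other reasons.

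**Working it through.** The point concerns a classification rule, and the plan states no figure to reproduce. The check follows one event through the texts: an AE that begins between consent and the start of infusion, is still present at infusion, worsens afterwards, and is kept as one record.

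1. **Can such an event arise?** Yes. AEs are collected from consent (Protocol 8.3.1). The interval can be up to 21 days (Protocol 4.6) and is at least 14 days at sites that send the eligibility sample to the central laboratory (Protocol 4.6.1.6). It can also be close to zero, because screening may be combined with the Day 0 baseline (Protocol 4.6.2).
2. **Treatment-emergent?** No. Its onset precedes the infusion, and onset is the only criterion in SAP 11.1 and Protocol 9.1.4.
3. **Causality?** Unrelated without assessment (Protocol 8.3.2 and 8.3.6).
4. **Suspected ADR?** No, because SAP 11.1 excludes anything labelled Unrelated.
5. **Infusional AE?** Unclear. SAP 11.1 and Protocol 9.1.4 refer to events during the infusion or within 24 and 72 hours after it. Neither says whether worsening in that window counts.
6. **Where does it appear?** In the non-TEAE summary and in the listing of all AEs (SAP 11.1).

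Next, whether another rule brings the worsening back in:

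- **AE form.** Protocol 8.3.6 lists onset, resolution, severity and causality for an AE entry. It gives no instruction to open a new entry when severity rises.
- **Change in intensity.** SAP 11.1 and Protocol 9.1.4 ask for the time of a material change in intensity, but only for AEs that occur during the infusion. The time is listed or tabulated; the event is not reclassified.
- **Physical findings.** The assessment asks whether existing findings have worsened (SAP 11.4). However, SAP 11.4 and Protocol 9.1.4 carry clinically relevant findings forward as AEs only if they were absent at baseline. Protocol 8.2.3 has no such limit, so a rash already present at baseline is not clearly covered.
- **Vital signs and laboratory values.** A large enough change from baseline is reported as an AE (Protocol 8.2.2), and laboratory deviations are judged against the subject's own baseline (Protocol 8.3.6). Protocol 8.3.6 closes this route when the abnormality is a known sign of a diagnosis already reported as an AE.

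No rule therefore requires the worsening to be counted. Some routes allow it.

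**Weight of one subject.** Each cohort has 11 planned subjects (Protocol 9.2, SAP 4.3). If all are infused:

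- one cohort: 1/11 = 9.1%
- both cohorts: 1/(11 + 11) = 1/22 = 4.5%

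These are the sizes of one affected subject in a table, not estimates of how many will be affected.

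**The case against.** The strongest reply is that the plan is silent on worsening rather than opposed to it. The AE definition in Protocol 8.3.1 is broad enough to cover a post-infusion aggravation, and nothing forbids a second entry. Entered separately, the worsening would be a TEAE and would receive a causality assessment. The eCRF completion instructions, which are not among the documents, may already require this. Staff ask about change at each visit, and Protocol 8.3.5 shows that its authors had worsening in mind for elective hospital admissions. All of this stands. It means that the outcome depends on site practice or on material not seen here.

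Four stronger readings are tempting and are not supported:

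- *That aggravation by the product can never reach the TEAE or suspected-ADR tables.* A separate entry is open to the investigator. Fever is a poor example, because a temperature change of at least 1°C from baseline is reportable as an AE in its own right (Protocol 8.2.2).
- *That the classification rules can only undercount.* The same part of SAP 11.1 applies the SAP 8.1 date algorithm, which treats unknown date parts as late as possible and so moves uncertain onsets towards TEAE. That shift has nothing to do with worsening, so it does not repair the gap.
- *That all safety conclusions rest on the TEAE and suspected-ADR tables.* Non-TEAEs, SAEs, discontinuations, allergic and thrombotic events, vital signs and laboratory shifts are summarised or listed as well (SAP 11.1 to 11.3). SAEs are reported whatever their attribution (Protocol 8.3.7).
- *That 9.1% or 4.5% is an expected bias.* The documents give no frequency for such events.

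**Conclusion.** The point holds in a limited form. For a pre-existing AE that worsens after infusion and is kept as one record, the stated rules give non-TEAE, Unrelated and not a suspected ADR, whatever the degree of worsening. Its place in the infusional-AE summaries is undetermined. The event is still visible in the non-TEAE summary and the all-AE listing, so it is misplaced rather than lost, but its causality stays preset and is never assessed. Two sites could classify the same course of events differently.

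The size is unknown. One subject is 9.1% of a cohort or 4.5% overall, assuming that 11 subjects per cohort are infused. The conclusion also assumes that no eCRF instruction outside these documents already requires a new entry. The change should be made, because the trial is first-in-human and its adult safety review comes before pediatric enrolment.

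**What to change.** - **SAP 11.1 and Protocol 9.1.4:** define a TEAE as an AE with onset at or after the start of infusion, or a pre-existing AE that worsens in severity or becomes serious at or after that time.
- **Protocol 8.3.2 and 8.3.6:** require the worsening to be recorded as a new AE entry with its own onset, severity and investigator causality assessment. Limit the automatic Unrelated label to the pre-infusion episode.
- **CRF completion instructions:** add a line to the same effect, so that all sites record worsening in the same way.

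Once the worsening has its own onset time, the existing 24-hour and 72-hour windows apply to it, which settles the infusional-AE question.

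The cost is a few sentences in the SAP and protocol, one CRF instruction, and a TEAE count that may be slightly higher. Sample size, dosing and visits do not change.

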## 8 CONCOMITANT MEDICATION AND TREATMENT

### 8.1 Prior and Concomitant Medication

All medications as documented by the investigator will be coded using Anatomical Therapeutic Chemical (ATC) classification codes via the World Health Organization Drug classification Dictionary (WHO-DD). All medications will be summarized by adult and pediatric populations and overall and sorted alphabetically by medication class (i.e., ATC level 2) and medication sub-class (i.e., ATC level 4). If the ATC level 4 term is missing, the ATC level 3 term will be used in the medication summary table and data listing.

The following convention will be used for missing or partial end date information in order to determine whether a medication is prior or concomitant:

The unknown portions of a medication end date will be assumed to be as late as possible. If a medication end date is incomplete but the month/year of medication end date is prior to the month/year of the start of study treatment, then the medication will be considered a prior medication. If a medication end date is incomplete but the month/year of medication end date is the same as the month/year of the start of study treatment, then the medication will be considered a concomitant medication. All other incomplete medication end dates and all medications with missing end dates will be assumed to be concomitant medications. Start/end dates reported in the eCRFs will be presented in the listings.

Prior medications are defined as any medication ended prior to the start of study treatment (i.e., start of the infusion on Day 0).

Concomitant medications are defined as any medication started on or after the start of study treatment or any medication taken prior to the start of study treatment and continued after the start of study treatment during the study.

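### The rule for incomplete AE start dates ignores the AE's recorded end date, so an event that resolved before infusion can be counted as treatment-emergent

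*SAP*

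**What the plan says.** SAP section 11.1 classifies AEs by comparing onset with the start of study treatment and gives this definition: "A TEAE will be defined as an AE which occurred on or after the start of study treatment". For partial or missing onsets it does not write a rule of its own: "For AEs with incomplete start dates, the same algorithm for missing or partial date information described in Section 8.1" is to be used.

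SAP section 8.1 (Prior and Concomitant Medication) is worded throughout for the end of a medication:

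- General principle: "The unknown portions of a medication end date will be assumed to be as late as possible".
- A partial end date falling before the "month/year of the start of study treatment, then the medication will be considered a prior medication".
- A partial end date whose month and year "is the same as the month/year of the start of study treatment, then the medication will be considered a concomitant medication".
- Everything else: "All other incomplete medication end dates and all medications with missing end dates will be assumed to be concomitant medications".

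Neither section mentions the AE's end date. Protocol section 8.3.6 makes the date and time of resolution a required AE entry, alongside onset. Protocol section 4.6.1.13 collects AEs from consent, and section 4.6 places screening up to 21 days before Day 0. On causality, Protocol section 8.3.2 adds: "Any AE experienced by the subject prior to the investigational product infusion on Day 0 will be labeled as Unrelated".

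**The concern.** An end-date rule suits medications. A drug still being taken at infusion is concomitant whenever it was started, so the end date is what settles its class. For an AE the class depends on onset. When onset is uncertain, the most useful remaining evidence is often the resolution date, because an event that ended before infusion must have started before infusion. The borrowed rule discards that evidence and can return the opposite answer.

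The TEAE tables are at stake: overall, by severity and by seriousness. The SAP summarizes TEAEs and non-TEAEs separately, so a misclassified event is added to one set of tables and lost from the other. With about 11 subjects per age group, a single subject is visible in a percentage.

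**Working it through.** The plan gives no figure to reproduce. The check applies the section 8.1 rule to AE onset and compares the result with the section 11.1 definition.

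**Rule carried over to AE onset.** Month and year before the infusion month: non-TEAE. Same month and year: TEAE. Any other incomplete date, or a missing one: TEAE.

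**Test cases.** The dates are assumed for illustration, with infusion on 20 March. The last column first applies the check that an AE with a recorded end before infusion is non-TEAE.

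| Recorded onset | Recorded end | SAP rule | With end-date check |
|---|---|---|---|
| March, day unknown | 10 March | TEAE | non-TEAE |
| February, day unknown | 10 March | non-TEAE | non-TEAE |
| Wholly missing | 10 March | TEAE | non-TEAE |
| Year of infusion only | 10 March | TEAE | non-TEAE |
| March, day unknown | none recorded | TEAE | TEAE |

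Three of the five classes change. In each of the three, the record shows that the event was over ten days before infusion, so it cannot meet the section 11.1 definition. The last row keeps the cautious default because nothing in the record contradicts it.

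**Can such events arise?** Yes, because collection starts at consent. With a full 21-day window and infusion on day d of a month, min(d − 1, 21) of the 21 preceding days share the infusion month. Averaged over a 30-day month:

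(0 + 1 + … + 21 + 8 × 21) / (30 × 21) = (231 + 168) / 630 = 399 / 630 = 0.63

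Counting every infusion date in a calendar year gives 0.64. This shows only that the same-month condition is commonly met. It is not a misclassification rate.

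**Size per subject.** SAP section 4.2 defines the Safety population as all infused subjects. SAP section 4.3 plans 11 adults and 11 pediatric subjects. If all are infused:

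- one age group: 1/11 = 9.1 percentage points
- overall: 1/22 = 4.5 percentage points

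These are upper limits for one misclassified subject. SAP section 11.1 counts a subject once per system organ class or preferred term, so a subject already counted in the category adds nothing.

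**The case against.** The strongest defense has four parts.

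- **The definition governs.** It stands in the same paragraph as the cross-reference, so the partial-date rule could be read as settling only cases that the record leaves open. A careful programmer might do this. The text, however, sends AEs with incomplete start dates to section 8.1 without that limit. One could also try applying section 8.1 to the AE's own end date, but section 11.1 classifies by onset, and section 8.1 has no step for a complete end date paired with an incomplete start.
- **Defaulting to treatment-emergent is conservative.** This stands where timing is unknown. It does not cover events whose recorded end settles the timing.
- **The trigger is rare.** Onset and resolution are both required entries, and AEs are assessed at screening and again at baseline. Screening may also be combined with the Day 0 baseline (Protocol section 4.6.2), which shortens the window. This stands, and it keeps the point minor.
- **Nothing false is displayed.** The borrowed rule is used only to set the class. The SAP does not say that an imputed onset is stored or shown, so a reader should not infer that listings will carry onsets later than the event's end. The tables would still use the wrong class.

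The year-only case is a side issue. For a year before the infusion year, the latest-possible principle in section 8.1 points to prior, while its catch-all sentence points to concomitant. An onset in the previous year and within the 21-day window requires infusion by 21 January and an entry lacking both day and month.

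**Conclusion.** The rule is wrong as written, and the consequence is small. SAP section 11.1 can class as treatment-emergent an AE that the record shows ended before infusion, against its own definition. No end-date check appears elsewhere in the SAP or protocol. The error can only over-count TEAEs. It adds at most 9.1 points per misclassified subject in an age group of 11, or 4.5 points in 22 overall, assuming all planned subjects are infused. The documents give no count of incomplete AE dates, so the total effect is unknown and probably slight.

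Four stronger readings are not supported:

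- **Most pre-infusion AEs with a missing day would be misclassified on the record.** The 63–64% share covers all pre-infusion days, not AEs with a known end before infusion.
- **Each event costs 10 points.** Ten is the evaluable target per age group. TEAEs are reported on all infused subjects, with 11 planned.
- **Suspected ADRs are inflated.** Pre-infusion AEs are labeled unrelated under Protocol sections 8.3.2 and 8.3.6, so these counts are largely protected.
- **The decision to open pediatric enrollment is affected.** Protocol section 9.1.5 and SAP section 4.4 set no TEAE-rate threshold for it, and over-counting would lean against opening. An effect is not shown.

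**What to change.** In SAP section 11.1, replace the cross-reference to section 8.1 with:

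*An AE with an incomplete or missing start date is treatment-emergent unless the known parts of its start date, or its recorded end date/time, show that it started or ended before the start of infusion.*

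This keeps the cautious default for onsets that are truly uncertain, including AEs whose end is missing or too incomplete to settle the matter. It also resolves the year-only conflict for AEs. The cost is one sentence and a small change to the TEAE derivation. No new data are needed, and the medication rule in section 8.1 stays as it is.
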